6. ENDPOINTS AND COVARIATES

6.1. Safety Endpoints

- Adverse drug reaction: Adverse events related to Genotropin, as judged by the physician or company.
- Adverse event: Adverse events, all-causality.
- Laboratory test

6.2. Efficacy Endpoints

- Height.
- Height SDS: $(\text{height} - \text{standard height for chronological age/gender}^2) / \text{standard deviation}$.
- Height velocity: $365.25 \times (\text{height} - \text{height of 1 year before}) / (\text{date of height measurement} - \text{date of height measurement of 1 year before})$ (height of 1 year before: Height of the previous year as used according to “[Appendix A1.3](#) Definition of timing for visit 3”).
- Height velocity SDS: $(\text{height velocity} - \text{mean height velocity for chronological age/gender}^3) / \text{standard deviation}$.

CCI

- [REDACTED]
- [REDACTED]
- [REDACTED]

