5.3. Other Analysis Sets

Set of patients who reached adult height (near final height).

The set of patients who reached adult height (near final height) is defined as a set of patients in the efficacy analysis set for whom adult height (near final height) was measured. Adult height (near final height) is defined as height after the time point that any of the following conditions is met.

- a. Annual height velocity of less than 2 cm after the maximum growth by puberty.¹
- b. Bone age of 17 years or older for males and 15 years or older for females.¹
- c. Reason for discontinuation in patient's profile of "reaching adult height (near final height)" or "epiphyseal closure".

Set of patients who did not reach adult height (near final height).

The set of patients who did not reach adult height (near final height) is defined as a set of patients in the efficacy analysis set who meet all the following conditions at the discontinuation of treatment and for whom height was measured at least once on Day 91 after the discontinuation of treatment or later.

- a. No puberty.
- b. Annual height velocity of 2 cm or higher after the maximum growth by puberty.
- c. Bone age of less than 17 years for males and less than 15 years for females.
- d. Reason for discontinuation in patient's profile of "reaching the standard height," "growth rate," "preference of patient/parent(s)," "non-compliance," "discontinuation of public funding," "change in diagnosis," "poor clinical response," "adverse event," "laboratory abnormal," or "others".

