8.2.4.2. Change in Height SDS

The summary statistics of measured values of height SDS at each age will be calculated for the efficacy analysis set and eligible criteria set. The evaluation points are according to [Appendix A1.1](#) Definition of timing for visit 1. The change in height SDS will be plotted with a solid line for individual male and female patients separately, with age on the horizontal axis and height SDS on the vertical axis. The start of treatment will be indicated as ▲, pubescence as ●, and reaching adult height (near final height) as ▼. They will be plotted with a dotted line after the completion/discontinuation of treatment.

The same calculation will be performed to prepare plots in the same manner for the set of patients who reached adult height (near final height) and set of patients not reached.

The summary statistics of measured values of height SDS at each evaluation point and change from the start of Genotropin will be calculated for a set of patients who reached adult height (near final height). The 95% confidence interval of the mean of the change will be calculated. The evaluation points are according to [Appendix A1.2](#) Definition of timing for visit 2. The change in height SDS will be plotted with a solid line for individual male and female patients separately, with evaluation points on the horizontal axis and height SDS on the vertical axis. The start of treatment will be indicated as ▲, pubescence as ●, and reaching adult height (near final height) as ▼. They will be plotted with a dotted line after the completion/discontinuation of treatment.

The summary statistics of measured values of height SDS at each evaluation point and changes from the start of Genotropin will be calculated in the efficacy analysis set and eligible criteria set. The 95% confidence interval of the mean of the change will be calculated. The evaluation points are according to [Appendix A1.3](#) Definition of timing for visit 3. The change in height SDS will be plotted with a solid line for individual male and female patients separately, with evaluation points on the horizontal axis and height SDS on the vertical axis. The start of treatment will be indicated as ▲, pubescence as ●, and reaching adult height (near final height) as ▼. They will be plotted with a dotted line after the completion/discontinuation of treatment.

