11. APPENDIXES

11.1. Appendix 1: Details of Data Extraction

A1.1 DEFINITION OF TIMING FOR VISIT 1

Timing for visit	Endpoint	Definition [allowable range]
3 years	Height Height SDS Body weight SDS BMI SDS IGF-I SDS	3 years and 0 month to 3 years and 11 months
4 years	Height Height SDS Body weight SDS BMI SDS IGF-I SDS	4 years and 0 month to 4 years and 11 months
N years	Height Height SDS Body weight SDS BMI SDS IGF-I SDS	N years and 0 month to N years and 11 months

The measured value on the latest date will be used when the same patient receives more than one measurement during the same visit.

A1.2 DEFINITION OF TIMING FOR VISIT 2

Timing for visit	Endpoint	Definition [allowable range]
Start of Genotropin therapy	Height SDS Body weight SDS BMI SDS IGF-I SDS	90 days before the first date of treatment (the start date of treatment) to the start date of treatment for this investigation
Pubescence	Height SDS Body weight SDS BMI SDS IGF-I SDS	The date evaluated as the pubescence +90 days
At reaching adult height (near final height)	Height SDS Body weight SDS BMI SDS IGF-I SDS	The date evaluated to reach adult height (near final height) +90 days

The measured value on the earliest date will be used when the same patient receives more than one measurement during the same visit.

In this regard, all the data measured after reaching adult height (near final height) will be used if plots are prepared.

A1.3 DEFINITION OF TIMING FOR VISIT 3

Timing for visit	Endpoint	Definition [allowable range]
Start of Genotropin therapy	Laboratory test parameters Height SDS Height velocity Height velocity SDS Body weight SDS BMI SDS IGF-I SDS	90 days before the first date of treatment (the start date of treatment) to the start date of treatment for this investigation
1 year later	Laboratory test parameters Height SDS Height velocity Height velocity SDS Body weight SDS BMI SDS IGF-I SDS	365 ±90 days after the start of treatment
2 years later	Laboratory test parameters Height SDS Height velocity Height velocity SDS Body weight SDS BMI SDS IGF-I SDS	730 ±90 days after the start of treatment
N years later	Laboratory test parameters Height SDS Height velocity Height velocity SDS Body weight SDS BMI SDS IGF-I SDS	365 × N ±90 days after the start of treatment
Completion of Genotropin therapy	Laboratory test parameters Height SDS Height velocity Height velocity SDS Body weight SDS BMI SDS IGF-I SDS	Final date of treatment for this investigation (completion date of treatment) ±90 days

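### Height SDS at adult height uses the chronological-age standard, which tends to overstate the gain in short patients who finish growing before the reference population

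*SAP*

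**What the plan says.** - **Definition of the score.** SAP 6.2 defines height SDS as height minus the "standard height for chronological age/gender", divided by the standard deviation. The visible text applies this at every visit and gives no adult reference or upper age limit.
- **When adult height is declared.** SAP 5.3 states: "Adult height (near final height) is defined as height after the time point that any of the following conditions is met". The three conditions are annual velocity below 2 cm after the pubertal maximum, "Bone age of 17 years or older for males and 15 years or older for females", and a discontinuation reason of adult height or epiphyseal closure. None sets a minimum chronological age.
- **Which height is used.** The adult-height row of Appendix A1.2 is "The date evaluated to reach adult height (near final height) +90 days". Below that table: "The measured value on the earliest date will be used when the same patient receives more than one measurement during the same visit".
- **What is reported.** For the adult-height set, SAP 8.2.4.2 summarises height SDS and its change from the start of treatment at the A1.2 visits, and adds: "The 95% confidence interval of the mean of the change will be calculated".
- **Later heights.** Protocol 5.5.3 and 6.8 restrict the Height Follow-up Form to patients who have not reached adult height. A1.2 uses all later heights in plots, but not in the table.

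**The concern.** Adult height is meant to be an end position, but the score attached to it depends on the patient's age that day. If a patient has stopped growing and same-age peers have not, the SDS is high on that day. It then falls as the reference mean rises, although the patient's height has not changed. Taking the first criterion met and the earliest measurement both favour a younger age, where the reference has more growth left.

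At stake is the size of the SDS gain to adult height. The investigation is exploratory, with no significance level (SAP 4.1) or decision rule (SAP 4.2), so no test is affected. The descriptive estimate and its interval are what would be published, and the interval does not reflect an error of this kind. Raw height (SAP 8.2.4.1) is unaffected. Height SDS by age (Appendix A1.1) is a legitimate description at that age.

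**Working it through.** The documents give no expected gain, reference mean or reference SD, so there is no figure of the plan's own to reproduce. The check is algebra on the SAP 6.2 formula, followed by assumed values.

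**Symbols**
- u = measured height minus reference mean at the patient's age
- D = adult reference mean minus reference mean at that age
- r = the patient's own growth after adult height is declared
- sa, sA = reference SD at that age and at adult age

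**Formulas**
1. SDS under the plan: u/sa.
2. SDS of true final height on the adult standard: (u + r - D)/sA.
3. The SDS at the start is the same in both, so it cancels from the change. Error in the gain = u/sa - (u + r - D)/sA = u(1/sa - 1/sA) + (D - r)/sA.
4. With sa = sA = s, this is (D - r)/s.

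**Sign.** For a patient below the mean (u < 0) with sa at least sA, the first term is zero or positive. With r < D, the second is positive. Under those conditions the gain is overstated. Outside them the sign is not fixed.

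**Assumed examples, u = -12 cm**

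| sa, sA (cm) | D (cm) | r (cm) | Plan SDS | Final SDS, adult standard | Error |
|---|---|---|---|---|---|
| 6, 6 | 1 | 0 | -2.00 | -13/6 = -2.17 | +0.17 |
| 6, 6 | 3 | 0 | -2.00 | -15/6 = -2.50 | +0.50 |
| 6, 6 | 5 | 0 | -2.00 | -17/6 = -2.83 | +0.83 |
| 6, 6 | 3 | 2 | -2.00 | -13/6 = -2.17 | +0.17 |
| 6, 6 | 2 | 2 | -2.00 | -12/6 = -2.00 | 0.00 |
| 6, 6 | 1 | 2 | -2.00 | -11/6 = -1.83 | -0.17 |
| 7, 6 | 3 | 0 | -1.71 | -15/6 = -2.50 | +0.79 |
| 5, 6 | 1 | 0 | -2.40 | -13/6 = -2.17 | -0.23 |

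**Effect on the cohort mean.** If a share p are early finishers with r = 0, SDs are equal at 6 cm and the rest have no error, the shift is p × D/6. With p = 0.25:
- D = 1 cm: 0.25 × 1/6 = +0.04
- D = 3 cm: 0.25 × 3/6 = +0.13
- D = 5 cm: 0.25 × 5/6 = +0.21

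**Check on the remedy.** Scoring the same measured height on the adult standard gives (u - D)/sA. Its error against true final height is -r/sA. With r = 2 and sA = 6 this is -0.33, against +0.17 (D = 3), 0.00 (D = 2) and -0.17 (D = 1) under the plan. At equal SDs the adult standard is further from the truth whenever D < 2r. When r lies between 0 and D, the plan's error is zero or positive and the adult-standard error is zero or negative, so the two scores bracket the true value.

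**The case against.** The strongest objection is that the plan's endpoint is near-final height. The velocity criterion admits patients still growing at up to 2 cm a year, and the other two criteria set no limit on velocity. A growing patient compared with growing peers may be scored about right, and an adult standard would then understate the result. A change from a childhood score to an adult score also mixes two references. This stands. It argues against replacing the specified score, but not against showing a second one beside it.

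Three further points:
- **Redaction.** Three efficacy endpoints in SAP 6.2 and all of SAP 8.2.4.9 are blacked out, and reference 6, on target height, has no visible citation. An adult-standard measure may exist there. The point concerns a visible definition used in a visible analysis, so it remains, but the fix must be conditional.
- **Plots.** A later fall in SDS would show in the individual plots for patients with later heights. That is a partial safeguard: the table and interval keep the first value, and the Height Follow-up Form is not used once adult height is reached, so later heights may be few.
- **Size.** Every centimetre and SD figure used is an assumption. If patients are at or near the age where the reference stops growing, D is close to zero and overstatement from this source is negligible.

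**Conclusion.** The point holds as a tendency. In the adult-height set, the change in height SDS from the start of treatment will tend to be overstated for short patients who stop growing before the reference population does. The direction is certain only for a patient below the mean, with less growth left than the reference, and with a reference SD at that age no smaller than the adult SD. The illustrative cohort shift of +0.04 to +0.21 SDS rests on an assumed 25% share of early finishers, r = 0, a common SD of 6 cm, D from 1 to 5 cm, and no error in the other patients.

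A reader might infer more than the documents support:
- **That every early finisher's gain is inflated and the error cannot go the other way.** Near-final height allows further growth, and reference SDs may differ by age. The examples include errors of -0.17 and -0.23.
- **That the study's main efficacy result is wrong.** No primary endpoint is named, and height SDS is also summarised by age and by year on treatment. Only the adult-height row of A1.2 is clearly affected.
- **That the subset by time to pubescence is distorted.** SAP 8.2.4.8 asks for change in height SDS by the factors in 5.4, without tying it to the adult-height set or to A1.2.

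**What to change.** Add a sentence to SAP 6.2 or Appendix A1.2. For the adult-height row, report height SDS and its change from the start, with the 95% interval, also against the adult (oldest-age) sex-specific mean and SD of SAP reference 2. Name the age taken as adult. Keep the chronological-age score beside it, and base any conclusion about gain to adult height on both. If a redacted endpoint already does this, a cross-reference is enough.

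The cost is a small programming change and an extra table row, with no new patient data and nothing deleted. The adult-standard gain may be smaller than the one now planned. Because near-final height allows further growth, that row may understate the true final SDS, by r/s at the adult SD, and a footnote should say so. The footnote should also say that its change runs from a childhood reference to an adult one.

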6.3. Other Endpoints

Not applicable.

6.4. Covariates

There are no identified or potential covariates from the clinical study or other data on the safety or efficacy of Genotropin.

7. HANDLING OF MISSING VALUES

Any missing data on the seriousness, measures taken, and outcome of adverse events will be handled as “unknown” in summarizing data.

Measured values outside the acceptable range (Appendix 1) at each evaluation time point of the efficacy endpoints and clinical laboratory parameters will be handled as missing and missing data will not be imputed.

The procedure to handle uncleaned data is described below.

- Items with missing data: Missing data will be handled as missing (“unknown” for the category of classification variables) for both tabulation and listing.
- Items with inconsistent data: Inconsistent data will be handled as missing for both tabulation and listing. In this regard, however, a data handling list will be prepared separately.
- No signature: Descriptions in the report form without signature of the contract physician (or with signatures of other physicians than the contract physician) will be handled as missing for both tabulation and listing. No date or inconsistent date in the signature date section (eg, date of signature before or after the start date of treatment) will be considered to indicate that there is no signature on the report form.

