5.2. Data collection method

In this investigation, data will be collected with case report/verification forms provided by Pfizer Japan, Inc. (hereinafter, "Sponsor"). Upon completion of the assessment period and height follow-up period, each investigator shall promptly complete the report/verification forms, and submit them to Sponsor.

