5.4. Assessment period

5.4.1. Assessment period for newly-enrolled subjects

The fiscal assessment period of the year in which subject is enrolled will be defined as a period starting with the commencement of Genotropin therapy (which may be tracked back) and ending with the fiscal end. The fiscal assessment period of each subsequent year will be defined as the corresponding annual fiscal period.

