5.4.2. Assessment period for ongoing subjects

For patients transferring from "Genotropin Special Investigation - Investigation of Genotropin long-term use in patients with SGA dwarfism without epiphyseal closure," the initial fiscal assessment period will be defined as a period starting on the day following the final assessment of data recorded in the last booklet for "Genotropin Special Investigation - Investigation of Genotropin long-term use in patients with SGA dwarfism without epiphyseal closure" and ending with the fiscal end of the applicable year. The fiscal assessment period of each subsequent year will be defined as the corresponding annual fiscal period.

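### Minor, wrong as written: SAP section 7's only example of an inconsistent signature date covers every date except the treatment start day, so nearly every correctly timed signature fits it

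*SAP*

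**What the plan says.** SAP section 7 ends with three rules for data problems that cleaning has not resolved, introduced by "The procedure to handle uncleaned data is described below". The third concerns signatures. What is written on a form that the contract physician has not signed "will be handled as missing for both tabulation and listing. No date or inconsistent date in the signature date section" is then put on the same footing: an absent or inconsistent date counts as an absent signature. The one illustration of inconsistency is "date of signature before or after the start date of treatment) will be considered to indicate that there is no signature".

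The SAP's visit-timing tables (Appendix A1.2 and A1.3) use the term for a single day: "90 days before the first date of treatment (the start date of treatment".

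The protocol sets the timing of the forms. Under 5.2, once the assessment or height follow-up period is over, "each investigator shall promptly complete the report/verification forms, and submit them to Sponsor". Under 5.6 (3) the investigator signs or seals after all entries and corrections are finished, and under 5.6 (4) the form goes to the sponsor promptly after the period closes. A new patient's first period is one "starting with the commencement of Genotropin therapy (which may be tracked back) and ending with the fiscal end" (5.4.1). A transferred patient's first period is one "starting on the day following the final assessment of data recorded in the last booklet" of the preceding investigation (5.4.2). Height follow-up begins when treatment is completed or discontinued (5.4.3).

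**The concern.** Any date other than a given day lies either before or after that day. An example built that way does not separate acceptable signature dates from unacceptable ones. It also marks as inconsistent the dates that the protocol's own sequence produces, because a form signed after its period has ended is signed after treatment began. Neither document gives another reference date for the signature.

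At stake is the treatment of forms still unresolved when the data are tabulated. If the example guided the programming, contents of properly signed forms among these could be set to missing. If it did not, the SAP does not say which dates were accepted instead.

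**Working it through.** The plan gives no figure here to reproduce. The check compares dates.

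**Inputs**
- T, the treatment start day: one day (SAP Appendix A1.2 and A1.3).
- E, the end of the period a form covers: the fiscal end (protocol 5.4.1, 5.4.2).
- S, the signature date: on or after E for a correctly timed form (protocol 5.2, 5.6).
- Fiscal year 1 April to 31 March: an assumption. The documents do not define it, but protocol section 4 runs the investigation from April 2013 to March 2016.
- The patient is followed to each fiscal end: an assumption.

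**The example as a condition.** A form is flagged if S < T or S > T, that is, if S ≠ T. From 1 April 2013 to 31 March 2016 there are 365 + 365 + 366 = 1,096 days. For a treatment start within that span, 1,096 − 1 = 1,095 dates are flagged and one passes.

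**Days from treatment start to the end of the period (E − T)**, new patient starting on the first / last day of the enrolment fiscal year:

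| Enrolment fiscal year | Booklet 01 | Booklet 02 |
|---|---|---|
| 2013 | 364 / 0 | 364 + 365 = 729 / 365 |
| 2014 | 364 / 0 | 364 + 366 = 730 / 366 |
| 2015 | 365 / 0 | 365 + 365 = 730 / 365 (only if the investigation is extended) |

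The 366-day years reflect 29 February 2016. The ranges are 0 to 365 days for Booklet 01 and 365 to 730 days for Booklet 02. If the start is tracked back to before the enrolment year, the gaps are longer.

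**When a correct signature passes**
- Booklet 01: S ≥ E ≥ T, so S = T only if S = E = T. Treatment must start on the last fiscal day and the form must be signed that same day.
- Booklet 02: E − T is at least 365 days, so S > T always.
- Transferred patients and the Height Follow-up Form: these periods begin after treatment has started, so S > T.

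**Count.** Assume signing 0 to 90 days after the fiscal end (91 possible days) and 365 possible start days in fiscal 2013. For Booklet 01, 365 × 91 = 33,215 combinations, of which 1 passes. If signing is at least one day after the fiscal end, 365 × 90 = 32,850 combinations and none passes. For Booklet 02, none of 33,215 passes. These are counts of calendar combinations under the literal reading. They are not probabilities and do not measure bias.

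**With a usable lower limit.** If only signatures dated before the end of the period were flagged, 0 of the 91 correctly timed Booklet 01 dates would be flagged. The same holds for the final assessment date in the booklet, which is no later than the end of the period.

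**The case against.** The strongest reply is that the rule is the general one about inconsistent dates and the disputed words are only a parenthetical example. A signature made after all entries and corrections is not inconsistent in any ordinary sense, and nothing shows that anyone would apply a reading that voids nearly every form. The rule also reaches only data left uncleaned after the sponsor queries, corrections and re-verification of protocol 5.6 (2) and (3). The guidance named in SAP 5.1 may hold the working convention. All testing is exploratory, with no significance level (SAP 4.1).

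Most of this stands, and it is why the point is minor. It does not rescue the example, which is the only indication of what inconsistent means and points the wrong way for the forms it reaches. SAP 5.1 cites the guidance for the analysis-set criteria, so whether it settles signature dates cannot be judged from these documents.

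A reader might infer three stronger conclusions. The documents support none of them.
- *The safety set would be emptied*, because voided forms leave no dose or adverse event information (SAP 5.1 c and d). This requires the literal reading to be applied to all forms, whereas the rule covers uncleaned data only, and the detail of those exclusions is left to the guidance.
- *Adverse events would drop out of the tables and listings.* This needs an unresolved form, voided on its date, in a patient who stays in the safety set, with an event recorded nowhere else. Protocol 6.7 has a separate prompt reporting route, and the SAP does not say whether the tables draw on it. The loss is possible but not established.
- *Voided forms would go unlisted.* The bullet on inconsistent items says "In this regard, however, a data handling list will be prepared separately". An inconsistent signature date can reasonably be read as falling under it. That the promise is not repeated in the signature bullet does not show exclusion.

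**Conclusion.** The example in SAP section 7 is wrong as written: it covers every date but one, and the protocol's timing places nearly every correct signature among the dates it calls inconsistent. The sole exception is a Booklet 01 whose period closes, and which is signed, on the treatment start day. This follows from the order of events in the protocol. The fiscal-year and signing-lag assumptions affect only the illustrative counts.

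The wording is probably a drafting or translation slip, perhaps a lost second reference date, although the documents do not say so. The practical effect is unknown, because it depends on how the rule was programmed and how many forms stayed uncleaned, and neither is given. No numerical bias can be derived and no decision rule is affected. The point is minor.

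**What to change.** Replace the parenthetical example with reference dates that can be met. For instance, a signature date is inconsistent if it is earlier than the final assessment or last observation date recorded in that booklet, or later than the sponsor's receipt of the final form or database lock. These limits are suggestions. The documents set none, and the sponsor should choose them.

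Check the new wording against the data-handling guidance named in SAP 5.1, and confirm before analysis that the programming follows it.

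Optionally, state that the data handling list already promised for inconsistent items also covers forms voided for signature reasons. This is a traceability preference and is not needed to cure the defect.

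The cost is one or two sentences of SAP text and one check of the programming, plus a further sentence if the optional statement is adopted. No new data are needed.
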